## CHAPTER 1 INTRODUCTION

The original purpose of the Infant Aphakia Treatment Study (IATS) was to assess the safety and the efficacy of IOL implantation in the rapidly growing eye of infants with a unilateral congenital cataract; children were randomized to either intraocular lens implantation (IOL) or contact lens (CL) correction following cataract surgery. Enrollment of the target sample size of 114 patients began in December 2004 and was completed in January 2009. Grating acuity was assessed at 12 months of age during Phase 1 of IATS and was completed in January 2010. Phase 2 began in March 2009. The optotype visual assessment was assessed during Phase 2 of the IATS when these children were age 4½ years using the ATS HOTV test. Phase 2 also included an ocular examination performed at age 5 years to evaluate: axial length, refractive error, keratometry, endothelial cell count, intraocular pressure, central corneal thickness and ocular alignment. At both the 1 Year and 4½ Year assessments, the visual acuity was found to be equal between the two groups. However, many more complications requiring additional surgery occurred in the IOL group, mostly in the first year after the initial surgery.

Glaucoma is one of the most serious adverse events that can develop after infantile cataract surgery. We did not find a significant difference in the cumulative incidence of glaucoma between the two treatment groups at age 5 years. We now postulate that newly diagnosed cases of glaucoma will occur more frequently between the ages of 5 and 10 years in the study eyes randomized to the CL group resulting in a higher cumulative incidence of glaucoma at age 10 years in this group. This hypothesis is based on a trend noted in the IATS between ages 1 and 5 years (new cases of glaucoma/glaucoma suspect: IOL group, 7 eyes (12%); CL group, 16 eyes (28%) and a study by Trivedi (Trivedi, 2006).

One of the unique challenges associated with primary IOL implantation during infancy is to select an IOL power that will optimize vision during infancy while not requiring an IOL exchange later in childhood. In the IATS, pseudophakic eyes were undercorrected by 8D (at 4-6 weeks of age) and 6D (at more than 6 weeks old) at the time of primary IOL implantation. At age 5 years, 3 eyes had undergone an IOL exchange because of a larger than expected myopic shift in the pseudophakic eye. We now postulate that additional pseudophakic eyes will require an IOL exchange after a longer follow-up. Following eyes randomized to IOL implantation to age 10 years, will allow us to identify risk factors for a large myopic shift and to determine the ideal undercorrection to optimize visual acuity while minimizing the need for IOL exchange. Phase 3 of this study intends to examine these children one additional time when they are 10 years of age. Longer follow-up will allow us to compare the long-term incidence and later onset of glaucoma in the study eyes in the two treatment groups and the rate of myopic shift so that risk factors for a larger than expected myopic shift can be identified in young children.

### **Study Aims:**

1. Compare the cumulative incidence of glaucoma between the two treatment groups at age 10 years to determine which initial treatment is associated with the lowest long-term risk of glaucoma or glaucoma suspect.
2. Characterize myopic shift between the ages of 5 and 10 years in the IOL group.
3. Examine the impact of Unilateral Congenital Cataract on reading (speed, accuracy and comprehension), self-esteem and Health Related Quality of Life i

## **Background**

At the time of our original proposal in 2003, IOLs were the accepted treatment following cataract surgery in older children and were being used increasingly in younger children (Wilson, 1996). However, among infants CLs were still the standard treatment since little was known about the safety of IOLs or the optimal IOL power to implant in a rapidly growing eye (Beller et al., 1981; Lorenz et al., 1991). Available data suggested that a fair-to-good visual acuity outcome could be more consistently obtained in infants with a unilateral congenital cataract who underwent IOL implantation at the time of cataract surgery (BenEzra, 1996; Dahan et al., 1997), but the methods used to assess the visual outcome in these series were non-standardized and may have overestimated the visual acuity of the pseudophakic eyes (Birch et al., 2005). Moreover, these series generally reported more complications in pseudophakic than aphakic eyes (Plager et al., 2002). Therefore, the question—What is the best way to treat infants with unilateral aphakia?—remained unanswered. The objective of IATS was to compare the visual outcome of two treatments for infants with a unilateral congenital cataract. The control group would receive the conventional treatment with a CL and later coupled with spectacle treatment. The experimental group would also undergo cataract surgery but in addition, would have an IOL implanted during the same surgery. The IOL would serve as the primary optical treatment. Any residual refractive error would then be corrected immediately with spectacles.

Given the expected 75-80 year life span of infants after cataract surgery and the impact that vision has on the quality of life, good vision in the cataractous eyes of children has the potential to have a major impact on their lives. Good vision in both eyes of these patients will allow them to pursue a broader range of professional and vocational opportunities and will give them the assurance that if they lose vision in their better seeing eye that they can continue to function as a sighted person. Reducing the incidence of glaucoma will also eliminate the discomfort and risks of having to undergo additional surgeries and/or daily medical therapy and the possible loss of vision in this eye later in life. While the prevalence of many complications can be established after a 5 year follow-up, the true prevalence of glaucoma following infantile cataract surgery cannot be established until after a longer follow-up. We chose a follow-up of age 10 years because most cases of glaucoma following infantile cataract surgery are diagnosed by this age. Thus, a 10-year follow-up of a well-characterized cohort should provide a more robust estimate of the impact of glaucoma on children treated for congenital cataract. In our own retrospective review of 62 eyes that underwent cataract surgery when <7 months of age, we found the 10-year risk of developing glaucoma or glaucoma suspect to be 63%.

The proposed research is expected to establish the optimal means of treating an infant following unilateral congenital cataract surgery to achieve the lowest incidence of glaucoma. In addition, exchanging an IOL requires that a child undergo general anesthesia with all of the attendant risks and costs. There are also ocular risks associated with additional intraocular surgeries. Accurately predicting the myopic shift after primary IOL implantation should reduce the need for IOL exchange.

Finally, the anesthesia associated with the standard care and treatment of surgical complications may result in a decrease in cognitive abilities. Children exposed to anesthesia before three years of age had lower scores in receptive and expressive language and cognitive ability than their peers (Ing et al.). Wilder et al. noted that children who had multiple anesthesia exposures prior to age 5 had significantly elevated risks of learning disabilities (Wilder). Another study noted that children who had surgery using general anesthesia within the first two years of life exhibited more behavior problems as teenagers.

IATS is a randomized clinical trial evaluating a large cohort of children who all underwent early cataract surgery using the same surgical protocols. After surgery, the children were examined at fixed time intervals using the same follow-up protocols. We had a 100% follow-up rate at age 12 months and a 99% follow-up rate at 5 years. In addition, the IATS developed a uniform definition of glaucoma with strict criteria. Intraocular pressure (IOP) was measured in all patients during an examination-under-anesthesia (EUAs) at age 12 months and at 4½ and/or 5 year examinations. Measuring IOP at follow-up examinations was made easier by the approval of ICare rebound tonometry (ICare Finland Oy, Helsinki, Finland) by the FDA in 2007. ICare rebound tonometry has been widely used in the IATS and it has greatly enhanced our ability to measure IOP in these young children in a clinic setting (Lambert, 2012). Previous studies reporting IOL implantation in infants have been small, retrospective case series (Autrata et al., 2005; Lundvall et al., 2006; Ram et al., 2011) with relatively short follow-up intervals and low follow-up rates. Finally, these other studies did not use a uniform definition of glaucoma and many relied exclusively on an elevated IOP to diagnose glaucoma. We expect the 10Y IATS visit to provide a more accurate assessment of the long-term effects of primary IOL implantation versus CL correction after unilateral cataract surgery during infancy on the cumulative incidence of glaucoma, the rate of axial length elongation, and the assessment of visual function.

In the Infant Aphakia Treatment Study (IATS), children with unilateral cataracts were exposed to anesthesia a minimum of two times in the first year of life as part of their standard of care. Many of these children had multiple other surgeries during this time period as a result of adverse events. For example, three-quarters of children in the IATS study had at least one additional surgery beyond the prescribed exam under anesthesia at twelve months of age, and over 90% of children who were randomized to receive an IOL at the time of cataract extraction had more intraocular surgeries as a result of adverse events, most commonly lens re-proliferation (68%) (Lambert et al, 2014). Before their fifth birthday, 44% of the IATS participants had had at least one additional surgery, not including surgery for strabismus (23-75%) and, to date, 3 of the 57 children randomized to remain aphakic had surgery to implant an IOL (Lambert et al, 2001).

### **Inclusion Enrollment Report**

We enrolled 114 children in IATS between 12/04 and 1/09. All study patients were between the ages of 28 and 210 days at the time of enrollment. The patients all had a unilateral congenital cataract and the fellow eyes were normal. Only infants were enrolled in the study because our goal was to compare two optical treatments for infants following infantile cataract surgery. The ethnicity and gender of the patients enrolled in IATS is shown in Table 7. The clinical trial is being conducted at 12 clinical sites. The DCC and the chairman's office are located at Emory University.

**Table 7: Ethnicity and Gender of Children Enrolled in IATS**

Gender	White	Black	Am Indian/ Alaska Native	Asian	Other	Total
Female	48	5	1	2	4	60
Male	49	3	0	1	1	54
Total	97	8	1	3	5	114

## **Procedures**

### **Glaucoma Evaluation**

The incidence of glaucoma and the best surgical approach to minimize its occurrence after infantile cataract surgery are not known. The objective of this hypothesis is to compare the cumulative incidence of glaucoma after unilateral congenital cataract surgery with or without IOL implantation after a much longer follow-up. Glaucoma is one of the most serious complications occurring after infantile cataract surgery. A wide range of incidences of glaucoma has been reported following infantile cataract surgery (9% – 32% in 7 studies).

One large population based study estimated that the cumulative incidence of glaucoma in children <9 months of age at the time of cataract surgery was 32% after a 10 year follow-up (Haargaard, 2008). However, all of these studies had serious limitations. All were retrospective and many had a selection bias. Furthermore, some studies defined glaucoma solely on the basis of an elevated IOP (>25 mmHg) (Cotter, 2003; Swamy et al., 2007). Studies which relied solely on an elevated IOP to diagnose glaucoma may have over-diagnosed glaucoma, since there can be a long “lag” phase between modestly elevated IOP and clinically significant optic nerve or visual field damage in eyes with healthy nerves. In addition, the thicker corneas of aphakic eyes introduces a controversial but important potential source of measurement error in using IOP alone as a criterion for diagnosing glaucoma (Simsek et al., 2006; Muir et al., 2007; Lupinacci et al., 2009; Lim et al., 2011). Lastly, some of these series included patients that had undergone cataract surgery using outdated surgical techniques that may be associated with a higher risk of glaucoma than surgery performed using modern surgical techniques (Phelps et al., 1977; Chen, 2004).

Most studies suggest that a follow-up much longer than 5 years is necessary to determine the true cumulative incidence of glaucoma in eyes undergoing cataract surgery during infancy. In a population based study from Denmark the median time interval between infantile cataract surgery and the diagnosis of glaucoma was 6.6 years (25% quartile, 1.1 years; 75% quartile, 10.7 years) (Haargaard, 2008). Others have reported a mean interval of 7 years or longer from the time of cataract surgery until glaucoma was diagnosed (Mills et al., 1994; McClatchey, 1997). One study reported that the cumulative incidence of glaucoma almost doubled (11% to 19%) between the ages of 5 to 10 years (Egbert, 2006). Most studies of aphakic glaucoma are limited by a relatively short follow-up and as a result likely underestimated the cumulative incidence of glaucoma (Swamy, 2007; Chak, 2008; Kuhli-Hattenbach et al., 2008).

There is a debate in the literature whether primary IOL implantation following cataract surgery reduces the risk of glaucoma in pediatric eyes. Two large retrospective multi-centered studies have reported that glaucoma rarely developed in children following cataract surgery and IOL implantation. In the first study, only 1 of 377 (<1%) pseudophakic eyes developed glaucoma (mean follow-up, 5.1 years) compared to 14 of 124 (11%) aphakic eyes (mean follow-up, 7.2 years) (Asrani et al., 2000). However, none of the pseudophakic children in this study underwent cataract surgery during the first 12 months of life and the pseudophakic patients were older than the aphakic patients at the time of cataract surgery (5.06 vs 2.73 years) suggesting a selection bias. In the second study, only 1 of 105 (1%) pseudophakic eyes developed glaucoma compared to 89 of 377 (23%) aphakic eyes (hazard ratio, 0.036; 95% confidence interval, 0.001, 0.914; p=.044) after a mean follow-up of 5.92 years (Mataftsi et al, In Press). While all of the patients in this study underwent cataract surgery during the first year of life (median age, 3 months), it is likely that there was a selection bias for the children undergoing IOL implantation since it was a retrospective, non-randomized study.

In contradistinction to the studies by Asrani (Asrani, 2000) and Mataftsi (Mataftsi, 2014), Trivedi and coworkers (Trivedi, 2006) did not find a statistically significant difference in the cumulative incidence of glaucoma after infantile cataract surgery with or without IOL implantation (24% vs 19%). However, the onset of glaucoma occurred earlier in eyes that underwent IOL implantation (median age of glaucoma onset, 3.5 months; range, 0.8 to 38 months) versus eyes that were left aphakic (median age of glaucoma onset, 90 months; range, 62 to 133 months). Glaucoma may develop earlier in infantile eyes after cataract surgery coupled with IOL implantation due to greater trauma to the trabecular meshwork at the time of cataract surgery. However, if glaucoma does not develop in the immediate postoperative period, the IOL may protect these eyes from developing glaucoma by mechanically supporting the trabecular meshwork or blocking the egress of toxic substances from the vitreous chamber to the trabecular meshwork. By following these children to age 10 years, we should be able to ascertain if the median age of onset of glaucoma is different between eyes that undergo primary IOL implantation versus eyes that are initially left aphakic after infantile cataract surgery.

### Phase 3 Definition and Diagnosis of Glaucoma:

In Phases 1 and 2, an eye was defined as having glaucoma if the following criteria were present: IOP >21 mmHg with one or more of the following anatomical changes: 1) corneal enlargement; 2) asymmetrical progressive myopic shift coupled with enlargement of the corneal diameter and/or axial length; 3) increased optic nerve cupping defined as an increase of  $\geq 0.2$  in the cup-to-disc ratio, or 4) the use of a surgical procedure for IOP control. An eye was defined as glaucoma suspect if any of the following criteria were present: 1) two consecutive IOP measurements >21 mmHg on different dates after topical corticosteroids had been discontinued without any of the anatomical changes listed above; or 2) glaucoma medications were used to control IOP without any of the anatomical changes listed above.

In Phase 3, an eye will be defined as having glaucoma if the following criteria are present: 1) IOP > 21mmHg; and 2) a progressive increase in cup-disc ratio, cup-disc asymmetry of  $\geq 0.2$ , or focal rim thinning. An eye will be defined as glaucoma suspect if any of the following criteria are present: 1) IOP > 21mmHg; or 2) glaucoma medications are being used to control IOP; or 3) an optic disc suspicious for glaucoma (e.g. increased cup-disc ratio). The criteria which will be used to diagnose glaucoma in Phase 3 will be the same as the criteria used in Phases 1 and 2 of the IATS, with the exception of ocular enlargement criteria. Unlike infants, children aged 5-10 years do not usually exhibit signs of ocular enlargement with elevated IOP. The criteria which will be used to diagnose glaucoma suspect in Phase 3 will also be the same as the criteria used in Phases 1 and 2 of the IATS with the exception that two consecutive IOP measurements >21 mmHg at two different visits will not be included in the definition since children in Phase 3 will only be examined once. In addition, since optic disc photographs will be taken at the 10Y exam, we have added a suspicious optic disc as another criterion for Phase 3. Since some children may be diagnosed as having glaucoma or glaucoma suspect between the five and 10 year evaluations, a review of medical records will be performed for all patients to determine who are classified as glaucoma or glaucoma suspect for Phase 3. This will assist in establishing diagnostic criteria and the age of onset for study purposes.

Adult glaucoma studies typically include visual field criteria for the diagnosis of glaucoma. We have chosen not to include visual field criteria for the following reasons: 1) children usually cannot perform visual field testing until they are about 7-10 years of age; 2) initial visual field testing is unreliable in children; and 3) at least three visual field tests are needed to document a reproducible visual field defect.

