### **Optic Disc Photos**

Stereoscopic disc photographs are an established means of evaluating optic discs for glaucomatous damage. All patients will have stereoscopic disc photographs taken after dilating the pupils. Dilation will be performed prior to obtaining optic disc photographs. Simultaneous stereo images centered on the optic disc should be performed on both eyes using a digital fundus camera. The resolution of the disc photos should be such that the disc margins and vasculature are clearly visible. Disc photographs will be reviewed independently by three ophthalmologists with expertise in pediatric glaucoma ([name], [name], and [name]). Photographs will be graded as normal, glaucoma suspect, or glaucomatous optic neuropathy primarily by comparing the appearance of the study eye to the fellow eye. Disc photographs were not part of the Phase 1 or 2 protocols due to the difficulty of obtaining high quality photographs in very young children.

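### A suspicious disc alone makes a case at 10 years but did not at 1 or 5 years, so a disc unchanged since before age 5 can be counted as arising at ages 5 to 10

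*Combined protocol and SAP*

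**What the plan says.** All references are to the combined protocol and SAP.

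**Phases 1 and 2** (Chapter 1, Phase 3 Definition and Diagnosis of Glaucoma). An eye was a suspect by one of two routes: "two consecutive IOP measurements >21 mmHg on different dates after topical corticosteroids had been discontinued", or "glaucoma medications were used to control IOP without any of the anatomical changes listed above". The disc entered only the glaucoma definition. There it had to be a change, "increased optic nerve cupping defined as an increase of" at least 0.2 in cup-to-disc ratio (C/D), accompanied by IOP above 21 mmHg.

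**Phase 3** (same section). Any one of three criteria makes an eye a suspect: IOP above 21 mmHg, glaucoma medication, or "an optic disc suspicious for glaucoma (e.g. increased cup-disc ratio"). The plan is open about the third being new: "since optic disc photographs will be taken at the 10Y exam, we have added a suspicious optic disc as another criterion for Phase 3".

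**Disc grading** (Chapter 4, Optic Disc Photos). Three ophthalmologists grade independently, "primarily by comparing the appearance of the study eye to the fellow eye". No earlier images exist for comparison: "Disc photographs were not part of the Phase 1 or 2 protocols".

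**Analysis** (Chapter 5, Statistical Analysis). The primary comparison is the percentage with glaucoma or glaucoma suspect by age 10, by Fisher's exact test. Time to the same endpoint is to be investigated with product-limit, log-rank and proportional hazards methods. Glaucoma alone is secondary.

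**Hypothesis** (Chapter 1, Introduction; repeated in Chapter 5, Glaucoma). The expectation is worded as follows: "newly diagnosed cases of glaucoma will occur more frequently between the ages of 5 and 10 years in the study eyes randomized to the CL" (the contact lens arm).

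**The concern.** The hypothesis concerns cases that arise between 5 and 10 years, and the plan places it beside 5-year rates obtained under the older definition. A criterion that enters only at 10 years, and asks for asymmetry with the fellow eye rather than change over time, can turn an eye from non-case to case with nothing having happened to the eye.

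Two kinds of conclusion are exposed. One is any statement about how much glaucoma or suspect status arose after age 5. The other is age of onset, which the background says the study should be able to compare between arms: a long-standing disc first labelled at the 10-year visit enters the survival analysis as a late event.

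The added disc criterion is not the only break in comparability. The Phase 3 suspect rule no longer asks for raised IOP on a second date. The Phase 3 glaucoma rule drops ocular enlargement and accepts C/D asymmetry or focal rim thinning.

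**Working it through.** **1. The plan's own figures.** Chapter 5, Glaucoma gives 16% (IOL) against 9% (CL) at 1 year, p = 0.39. With 57 per arm these are 9/57 and 5/57, and the two-sided Fisher test gives p = 0.393, as stated. The 5-year figures of 28% and 35% are 16/57 and 20/57. For IOL, 9 cases at 1 year plus the 7 new cases in the Introduction make 16. For CL, 5 + 16 = 21, one eye more than 35% implies; this does not affect the argument. Eyes that were non-cases at 5 years: 57 − 20 = 37 (CL) and 57 − 16 = 41 (IOL).

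**2. The rules applied to three hypothetical records, IOP 14 mmHg throughout.**

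| Record | Phase 1 and 2 rules | Phase 3 rules |
|---|---|---|
| Study eye C/D 0.5, fellow 0.3, at 1, 5 and 10 years | non-case | can be suspect (disc only) |
| Study eye C/D rises from 0.2 to 0.5 | non-case (IOP not raised) | can be suspect (disc only) |
| Symmetric, unchanged discs | non-case | non-case |

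The first eye did not change after age 5; only the definition did. The second did change, but was not a case under the older rules either. A truly constant definition therefore leaves both out, and the second kind needs its own line in the report.

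**3. Effect on the apparent rise since age 5.** Let f be the share of remaining non-cases called suspect on a long-standing disc alone. The documents give no value; 5 to 20% is assumed. With no true new cases, the apparent rise is f × 37/57 in CL and f × 41/57 in IOL.

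| f | CL | IOL |
|---|---|---|
| 5% | 1.85/57 = 3.2 points | 2.05/57 = 3.6 points |
| 10% | 3.7/57 = 6.5 points | 4.1/57 = 7.2 points |
| 20% | 7.4/57 = 13.0 points | 8.2/57 = 14.4 points |

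**4. Effect on the arm difference at 10 years.** With true 10-year risk p, the observed risk is p + (1 − p)f. If f is equal in both arms, the difference becomes (pCL − pIOL)(1 − f).

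Illustration, with assumed true conversion after age 5 of 30% in CL and 5% in IOL:
- pCL = (20 + 0.30 × 37)/57 = 31.1/57 = 54.6%
- pIOL = (16 + 0.05 × 41)/57 = 18.05/57 = 31.7%
- true difference = 13.05/57 = 22.9 points

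| f, equal in both arms | Difference (points) | Fisher power (two-sided 0.05 assumed, 57 per arm) |
|---|---|---|
| 0 | 22.9 | 62% |
| 5% | 21.75 | 57% |
| 10% | 20.6 | 52% |
| 15% | 19.5 | 47% |

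If f differs by arm, the direction is not fixed. With 10% in CL and 5% in IOL, the risks are 54.56 + 45.44 × 0.10 = 59.1% and 31.67 + 68.33 × 0.05 = 35.1%. The difference widens to 24.0 points and power rises to 67%. With the rates exchanged it narrows to 18.3 points. The break-even ratio fCL/fIOL is (1 − pIOL)/(1 − pCL) = 68.33/45.44 = 1.50.

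**The case against.** **The primary test is sound.** It is cumulative to age 10, by intention to treat, and applies one definition to both arms; Chapter 4 describes masked review of the stereophotographs. It does not date cases to ages 5 to 10, and equal misclassification cannot create a false arm difference. All of this stands. A reader might infer that the added criterion necessarily shrinks the arm difference. The documents do not support that: it needs near-equal disc-only rates, which randomisation and masking make plausible but do not guarantee.

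**An unchanged disc might never be graded suspicious.** The protocol's example is an increased C/D, and the fellow eye is the main comparator, not the only one. This is why the claim is that such a disc can count, not that it will. The example is only illustrative and names no earlier value as reference, whereas the Phase 3 glaucoma rule does speak of progression.

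**The plan already has partial safeguards.** Glaucoma alone is analysed separately and requires IOP above 21 mmHg, so disc-only eyes are non-cases there. A three-category model separates suspects from glaucoma. Records are reviewed for classification and age of onset. The plan itself warns that survival analysis may be problematic. These help, but none isolates the disc-only eyes. The first discards every suspect, the second pools all routes to suspect status, and the third has no rule for a disc that pre-dates age 5. The plan's warning concerns missing diagnosis dates, not a changed definition.

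**The sizes are assumed.** Neither f nor the conversion rates are in the documents, so the tables show sensitivity and are not forecasts.

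**Conclusion.** The point holds for the comparison over time. As written, the plan can count a disc unchanged since before age 5 as a case arising at ages 5 to 10. It can thereby inflate the rise from 35% and 28% and misdate onset. At an assumed f of 5 to 10% this is about 2 to 4 eyes per arm, or 3 to 7 percentage points, with no true new disease. This part does not require f to be equal across arms.

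The effect on the primary comparison is secondary and conditional. With equal f the expected difference shrinks by the factor (1 − f), a loss of about one point in 22.9 at f = 5%. With unequal f it may move either way. The documents give no ground for calling the Fisher test invalid.

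The single-date IOP criterion and the altered glaucoma rule also separate the two definitions, so dropping disc-only eyes alone would not restore a constant definition. The calculations assume 57 per arm with complete follow-up.

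**What to change.** Keep the Phase 3 definition for the primary endpoint, and make four additions.

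1. On the eCRF, record which criterion or criteria each eye meets. Tabulate by arm the eyes that qualify only through the disc, and those that qualify only through raised IOP at one visit without a second date.
2. In Chapter 5, Statistical Analysis, pre-specify a sensitivity analysis that repeats the Fisher and time-to-event analyses with the Phase 1 and 2 suspect rules, as far as the 10-year visit and record review allow. Disc-only eyes are non-cases in it.
3. Report separately, by arm, the disc-only eyes whose C/D rose by at least 0.2 (the Phase 1 and 2 threshold) from a recorded Phase 1 or 2 value. Do not add them to the analysis in item 2.
4. Present any statement about the rise since age 5 or age of onset alongside that analysis, and say that the 5-year and 10-year definitions differ, including any difference in the glaucoma rule that remains.

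The cost is SAP wording, a few eCRF fields and one repeated set of analyses. The sensitivity analysis will have fewer cases and less precision. Earlier C/D values are implied by the Phase 1 and 2 rule, but their completeness is not documented, so item 3 may be partial.
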